OFFICIAL TITLE: Oral Health Educational Methods in Adolescence

NCT number: **03216746**

Date:17/07/2018

Study Protocol and Statistical Analysis Plan

Study population and sample size

The investigation followed the parameters of the Declaration of Helsinki and was approved by the Human Ethics Committee of the Federal University of Paraná (case number 51712315.4.0000.0102). The description of this clinical trial followed the recommendations made by CONSORT and the extension to cluster randomized trials¹⁹. The study was registered in the clinicaltrials.gov database under number NCT03216746.

Clinical trial randomized by clustering involving four arms in a 1: 1: 1: 1 ratio to the four intervention groups. The randomized allocation was performed using the classes as sample units. The courses were ordered alphabetically by name and allocation was generated by the software *Stata* version 12.0. A total of 28 classes were selected and randomly allocated to an interventional group by a blinded investigator, which did not participate in the study. The analysis was done in the individual unit. Adolescents of both sexes, aged 14 to 19 years, enrolled in a technical high school in the city of Curitiba, Paraná, Brazil were evaluated. Written informed consent was obtained prior to randomization from the participant or from the legal guardian when the age of the participant was less than 18 years.

Exclusion criteria were: adolescents with some physical or mental condition that made interventions impossible and those using fixed orthodontic devices at the time of clinical examination. Cluster unit areas of technical education related to the

health area, including dental technician, were excluded. The duration of the study was from July to December 2016.

The comparison between two independent groups was used for the sample calculation considering the unequal variances. For this calculation, the outcome was considered the "knowledge score" (KS). In a pilot study, it was found that the standard deviation of the KS from the "oral guidance" group was 2.56, while in the "video" group it was 1.96. In the same study, the difference detected between the groups was 0.53 points in the knowledge score. Therefore, considering a 5% significance level and 80% statistical power, a sample value of 108 individuals was found for each group, totaling 216 participants. Estimating a loss of 35% for each group, the final sample totaled 317 individuals.

Pilot study

A pilot study was carried out with the objective of testing the suitability and methodological applicability of the instruments used. In addition, this step allowed us to verify the application dynamics of the instruments and the average time spent with each participant. Fifteen adolescents aged 14 to 19 years, with the same socioeconomic characteristics as the study population, were selected who did not participate in the main study. The methodological design was adequate; however, some terms of the questionnaire were modified to allow greater understanding on the part of the adolescents.

Interventions

Interventions were performed at the individual level within each cluster. The study included four phases (Figure 1), and the educational interventions or their different associations were evaluated through the knowledge score (KS) and oral

clinical indexes. In Phase I/baseline, the participants answered a questionnaire (pre-test) and were evaluated clinically. In phase II, the 28 classes were randomly allocated into two groups: 14 classes received oral guidance (OG) and 14 classes received video guidance (VG). Both methods (oral guidance and guidance by video) had the same thematic content. In the next phase (III), the groups were again divided into four groups (7 groups in each group), and for two of them, a smartphone App was developed so that reinforcement messages were sent during a period of 30 days. Shortly after this period (phase IV), the participants answered the questionnaire again (follow-up test) and were reassessed clinically.

Oral guidance with standardized content was performed by one of the researchers (GM) previously trained, and included aspects on general, oral health and, especially, on periodontal diseases. This guidance was carried out in the classroom, in a group, with approximately 20 adolescents, providing an environment of discussions on the subjects addressed. The duration was approximately 15 minutes. The elaboration of the video had the participation of three actors, two acting as adolescents and the third as a dental surgeon. The video had a total duration of 14 minutes and was applied in the classroom itself, in a group, with approximately 20 adolescents, without, however, allowing a later discussion of the subject.

The "Oral Health" App was specially developed for this research and developed for the Android system version 4.4 (*Kitkat*) API level 19 with JAVA language (JDK 1.8.0) in the environment Android Studio 2.1.2, having 27.90 megabytes. The App has been made available for free on Google Play for 12,199 cellphone models. This tool was aimed at transmitting knowledge in oral health in a didactic, simple and relaxed way to its target audience over a period of 30 days. To this end, 60 messages were developed, based on the contents previously exposed in the educational activities, of which they were sent twice a day to each participant: the first with information in written form and the second in the form of videos, which had an average

duration of one minute, developed especially for this research and aiming to reinforce the content of the first tip.

The participant received messages developed through the Android notification bar. The standard tone and vibration of the phone were activated when receiving the messages. For the execution of these functionalities some permissions of the cellphone were necessary: permission to access the internet, to vibrate the cell phone, to keep the screen on while running the video and permission for the App start when the phone was turned on. The App performed its functions even when the cellphone was offline, requiring access to the Internet only at the time of downloading the App. The App source code can be obtained through the address in GitHub (<https://github.com/[name]/saudebucal>) and can be accessed and used by any user.

Questionnaires

Primary outcome was the knowledge score (KS) regarding etiology, treatment and forms of prevention of periodontal diseases. Data was obtained from a self-administered questionnaire, tested in a pilot study, using five statements: 1: If I have good oral hygiene I have less possibility of having gingival bleeding; 2: Whoever brushes their teeth very well does not need to floss; 3: It is not possible to remove the calculus or tartar with dental brushing; 4: Mouthwashes with mouth rinses may render flossing needless; and 5: A person may lose his teeth because he has problems in the periodontium. The answers were arranged in a three-point Likert scale, being *I agree*, *disagree* and *neither disagree nor disagree*. Correct answers were scored 1 (one), and incorrect and "do not know" score 0 (zero). Scores ranged from five (higher knowledge) to zero (less knowledge).

Those responsible for adolescents also answered a questionnaire containing socioeconomic and demographic information according to criteria of the Brazilian Association of Research Companies²⁰.

Oral clinical examination

Clinical examination was performed by a single examiner calibrated ($K \geq 0.83$) and blinded as to the intervention used and which verified the presence of dental biofilm through the simplified oral hygiene index (OHI-S)²¹ and gingival bleeding (GBI)²². The tests were performed in two stages: Phase I and 20 weeks after in Phase V (Figure 1). The subjects were examined in a classroom where they were seated in chairs, and the evaluations were done individually, using gauze, artificial light and a millimeter probe.

Statistical analysis

Statistical analysis was performed on an individual level. Chi-square test was used to analyze the categorical variables. The numerical variables were submitted to the *Kolmogorov-Smirnov* test to verify the normality of the data, obtaining values of $P < 0.05$. Thus, non-parametric tests were used to verify the association between the means of KS, OHI-S and GBI among the different intervention groups. The OHI-S variable was dichotomized in: $OHI-S > 1$ (high dental biofilm index) and $OHI-S \leq 1$ (low dental biofilm index). *Kruskal Wallis* and *Mann-Whitney* tests were used for independent samples and *Wilcoxon's* test for paired samples. The level of significance adopted for all analyzes was 5%. The analyzes were performed using SPSS software version 20.0 (SPSS Inc., Chicago, IL, USA).

[figure not shown]

Figure 1. Flow chart demonstrating the different phases of the study.

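### Baseline KS is collected before the 28 classes are allocated, but neither the allocation nor the between-arm tests use it, so chance baseline gaps pass into the follow-up comparison

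*Combined protocol and SAP*

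**What the plan says.** All references are to the combined protocol and SAP.

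- **Study population and sample size.** Classes are the unit of allocation, in four arms at 1:1:1:1. On method, the text says that "The courses were ordered alphabetically by name and allocation was generated by the software" Stata, carried out by a blinded investigator outside the study. Stratification, matching, blocking and constrained randomisation are not mentioned. The pupils are aged 14 to 19.
- **Interventions.** The order is explicit: "In Phase I/baseline, the participants answered a questionnaire (pre-test) and were evaluated clinically"; then "In phase II, the 28 classes were randomly allocated into two groups", 14 classes each. Phase III splits these into four groups of 7 classes.
- **Statistical analysis.** Testing is at the individual level: Kruskal-Wallis and Mann-Whitney between groups, and Wilcoxon for paired data. No baseline covariate is named for a between-group comparison.
- **Sample size inputs.** From the pilot, the KS standard deviations are 2.56 (oral guidance) and 1.96 (video), and "the difference detected between the groups was 0.53 points in the knowledge score".

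**The concern.** With few clusters, simple random allocation can leave arms with different starting knowledge by luck. Larger trials average this out; 7 classes per arm may not. Here the information needed to limit it is collected before allocation, at no extra cost, and the described procedure does not use it. Nor does the analysis step in later. The paired Wilcoxon test looks at change within a group, and the between-group tests are not described as using the pre-test. A baseline gap would therefore sit inside the estimated difference at follow-up, and a reader could not easily tell it from an intervention effect of similar size.

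**Working it through.** **Inputs from the document.** 28 classes; 7 per arm, or 14 per side for oral guidance v video; KS scored 0 to 5; pilot SD 1.96 (the smaller of the two); difference 0.53. Class size is 317/28 = 11.3, taken as 11, or about 20 from the description of the classroom groups.

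**Assumed, because the document gives none.** ICC 0 to 0.10; an alternative SD of 1.2; correlation between baseline and follow-up of 0.5 for pupils within class and 0.8 for class effects.

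**The plan's own figure.** The stated 108 per group does not reproduce. The named formula gives (2.56² + 1.96²)(1.960 + 0.842)²/0.53² = 291 per group, two-sided. That is a separate problem. Here 0.53 and 1.96 serve only as yardsticks.

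**Step 1: size of a chance baseline gap.** With k classes per side and m pupils per class,

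SD of gap = √[(2/k) × SD² × (ICC + (1 − ICC)/m)].

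For SD 1.96, k = 7, m = 11:
- ICC 0: √(0.2857 × 3.8416 × 0.0909) = 0.32
- ICC 0.10: √(0.2857 × 3.8416 × 0.1818) = 0.45

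The chance that the gap exceeds 0.53 in either direction is 2 × [1 − Φ(0.53/SD of gap)]. Each cell gives the SD of the gap, with that chance in brackets.

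| SD | Classes per side | Pupils per class | ICC 0 | ICC 0.05 | ICC 0.10 |
|---|---|---|---|---|---|
| 1.96 | 7 | 11 | 0.32 (9%) | 0.39 (17%) | 0.45 (24%) |
| 1.96 | 7 | 20 | 0.23 (2%) | 0.33 (11%) | 0.40 (18%) |
| 1.96 | 14 | 11 | 0.22 (2%) | 0.27 (5%) | 0.32 (9%) |
| 1.2 | 7 | 11 | 0.19 (0.6%) | 0.24 (2.5%) | 0.27 (5%) |
| 1.2 | 14 | 11 | 0.14 (<0.1%) | 0.17 (0.2%) | 0.19 (0.6%) |

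Simulated allocations agree to about one percentage point.

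**Step 2: what blocking does to the gap.** Rank the 28 classes on Phase I mean KS, form 7 blocks of four, and randomise one class per block to each arm. In simulation (11 pupils per class, 7 v 7), the SD of the gap falls to 0.09 to 0.13 at SD 1.96 and 0.05 to 0.08 at SD 1.2. Gaps above 0.53 almost vanish.

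**Step 3: what it does to the follow-up standard error.** The correlation between a class's baseline and follow-up means is

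r = [0.8 × ICC + 0.5 × (1 − ICC)/m] / [ICC + (1 − ICC)/m],

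which is 0.50, 0.61 and 0.665 at ICC 0, 0.05 and 0.10 with m = 11. Blocking leaves about (0.09/0.32)² = 8% of the baseline-gap variance, so the SE is multiplied by √(1 − 0.92r²) = 0.88, 0.81 and 0.77. That is a cut of 12%, 19% and 23% against simple allocation with no adjustment; simulation gives about 12% to 24%.

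**Step 4: the same gain from analysis alone.** Simple allocation followed by class-level adjustment for baseline KS multiplies the SE by about √[(1 − r²) × (1 + 1/22)], where the last factor is the cost of estimating one slope from 28 classes in four arms. This gives 0.89, 0.81 and 0.76, a cut of about 11% to 24%. In simulation, blocking on top of adjustment adds about 1 to 3 percentage points.

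**The case against.** The strongest reply is that nothing is invalid here. Classes are allocated at random by someone outside the study, so imbalance is a matter of luck, and a correct cluster-level standard error already includes it. That stands, and it limits the point to an improvement. Other replies also stand:

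- **Analysis can do most of the work.** A reader might infer that only balance at allocation can solve this. Step 4 shows otherwise for KS: the gain from blocking is measured against an unadjusted analysis, and baseline adjustment recovers nearly all of it.
- **Course and age.** A reader might infer that blocking on KS also protects against imbalance in course or age. It does not unless the blocks are formed on them, and the document gives no figure for their effect on KS.
- **The 0.53 yardstick.** This is the pilot difference between oral guidance and video. If the App arms are pooled, that contrast has 14 classes a side, and the 7 v 7 frequencies overstate its risk. They apply to comparisons of individual arms, for which no target difference is stated.
- **The pilot SD.** It comes from 15 adolescents and is large for a 0 to 5 score, whose population SD cannot exceed 2.5. At SD 1.2 large gaps are uncommon.
- **Silence.** The document shows that the pre-test was answered before allocation, not that it had been scored by class. The absence of balancing is inferred from its not being described.

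What the reply does not remove is that the described analysis makes no baseline adjustment, so as written neither safeguard is in place.

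**Conclusion.** The point holds as a cheap improvement to the design and analysis. As described, neither allocation nor analysis protects the between-arm comparison from a chance baseline gap. At the pilot SD of 1.96, a gap above 0.53 between two arms arises in about 9% to 24% of allocations with 11 pupils per class and about 2% to 18% with 20. At SD 1.2 and 11 pupils it is about 0.6% to 5%. For oral guidance v video at 14 v 14, it is about 2% to 9% at SD 1.96 and under 1% at SD 1.2. These figures rest on an assumed ICC of 0 to 0.10 and equal class sizes.

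A reader might take the alphabetical list to mean that allocation followed the alphabet, or that the results are systematically biased. The document supports neither: the list is the frame, and the assignment is described as random. The cost is lost precision and a less credible single result.

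**What to change.** **For a repeat or extension.** Once every class has finished Phase I, rank the 28 classes on mean KS and form 7 blocks of four. Have the independent investigator randomly assign one class per block to each of the four arms in a single list. State a class-level or cluster-adjusted analysis that includes the block or baseline KS. Form the blocks on course or age as well only if protection for those is wanted.

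**Cost.** A short script in the Stata step already used, with no extra pupils or measurements. Allocation must wait for all Phase I data, and the analysis must carry the block, which the named Kruskal-Wallis and Mann-Whitney tests do not do.

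**For the trial as run (July to December 2016).** Re-allocation is not available. Report baseline KS by arm, and adjust the follow-up comparison for baseline KS while allowing for class. Under the stated correlations this gives most of the same gain. If any balancing was used at allocation but not described, state it.

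### The stated 80% power with 108 per group does not follow from the plan's own inputs, ignores the randomisation of classes, and does not cover the four-arm or App comparisons

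*Combined protocol and SAP*

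**What the plan says.** All references are to the combined protocol and SAP.

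- **Study population and sample size, design.** "Clinical trial randomized by clustering involving four arms in a 1: 1: 1: 1 ratio to the four intervention groups". Classes are the randomised units, 28 of them.
- **Same section, sizing.** "The comparison between two independent groups was used for the sample calculation considering the unequal variances". From the pilot, "the standard deviation of the KS from the 'oral guidance' group was 2.56, while in the 'video' group it was 1.96", and "the difference detected between the groups was 0.53 points in the knowledge score". The result: "considering a 5% significance level and 80% statistical power, a sample value of 108 individuals was found for each group, totaling 216 participants". Then: "Estimating a loss of 35% for each group, the final sample totaled 317 individuals".
- **Interventions.** "In phase II, the 28 classes were randomly allocated into two groups", 14 classes to oral guidance and 14 to video. In phase III "the groups were again divided into four groups (7 groups in each group"), and two of the four receive the App. The follow-up test comes after that.
- **Questionnaires.** The knowledge score (KS), the primary outcome, runs from 0 to 5.
- **Pilot study.** Fifteen adolescents took part, and some questionnaire terms were changed afterwards.
- **Statistical analysis.** Individuals are the unit of analysis. KS and the clinical indices are compared across the intervention groups by Kruskal-Wallis and Mann-Whitney tests. No primary contrast is named.

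The plan gives no intraclass correlation (ICC), no design effect, no allowance for four arms and no expected App effect.

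**The concern.** The plan has one power statement. It describes two groups of independent individuals, but the trial randomises classes and ends with four arms of 7 classes. Three questions follow: whether 108 per group delivers 80% for the contrast it was computed for, whether that survives clustering, and whether it says anything about the four-arm and pairwise tests.

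The App is at stake. It enters only in phase III, so only comparisons among the four groups can judge it, and the calculation does not address them. If a reader carries the 80% across, a non-significant App result could be taken to show that the App adds nothing.

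**Working it through.** **Inputs from the documents.** SDs 2.56 and 1.96; difference 0.53; 5% level; 80% power; 108 per group, 216 in total; 35% loss; 317; 28 classes (14 v 14, then 7 per arm).

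**Assumptions.** Two-sided tests, since sidedness is not stated. A normal approximation stands in for the rank tests. ICC 0.02 to 0.10, since none is given. The 0.53 is used for every contrast, since it is the only effect given.

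**1. Reproduce 108.** The sum of variances is v = 2.56² + 1.96² = 6.5536 + 3.8416 = 10.395.

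n per group = (1.960 + 0.842)² × v / 0.53² = 7.849 × 10.395 / 0.2809 = 290.5, so 291. One-sided it is 229. Neither gives 108. Averaging the SDs gives 286 (225 one-sided), and treating the SDs as variances gives 127 (100 one-sided). A one-sample formula with SD 1.96 alone gives 107.3, which rounds up to 108, but that is not the two-group calculation described.

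Working back, 108 per group needs a common SD of √(108 × 0.2809 / (2 × 7.849)) = 1.39, below both stated SDs.

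**2. Power at 108.** The standard error is √(10.395/108) = 0.310, and 0.53/0.310 = 1.708. Power = Φ(1.708 − 1.960) = 40% (one-sided 52.5%).

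**3. Reproduce 317.** 216/0.65 = 332.3, so 333; 216 × 1.35 = 291.6, so 292. Neither is 317, which implies a loss of 1 − 216/317 = 31.9%. Conversely, 317 × 0.65 = 206, below the plan's own 216.

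**4. Evaluable numbers.** From 317: 206.05/4 = 51.5 per arm, 206.05/2 = 103 per side, 206.05/28 = 7.36 per class. From 216: 54 per arm.

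**5. Design effect.** DE = 1 + (7.36 − 1) × ICC = 1.127, 1.318 and 1.636 at ICC 0.02, 0.05 and 0.10.

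**6. Power at 0.53 points, on two premises.**
- Stated SDs: Φ(0.53/√(v × DE/n) − 1.960).
- Granting that 108 gives 80%: Φ(2.802 × √(n/(108 × DE)) − 1.960).

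| Contrast | n per side | Stated SDs | 108 granted as 80% |
|---|---|---|---|
| One pair of arms, no clustering | 51.5 | 22% | 49% |
| One pair of arms, no clustering | 54 | 23% | 51% |
| One pair of arms, ICC 0.02 / 0.05 / 0.10 | 51.5 | 20 / 18 / 15% | 44.5 / 39 / 33% |
| Pooled oral v video, no clustering | 103 | 39% | 78% |
| Pooled oral v video, ICC 0.02 / 0.05 / 0.10 | 103 | 35 / 31 / 26% | 73 / 66 / 57% |

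From the stated SDs, before clustering, the difference detectable with 80% power is 2.802 × √(10.395/51.5) = 1.26 points for a pair of arms, and 2.802 × √(10.395/103) = 0.89 points pooled.

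**7. Are the SDs credible?** A 0 to 5 score has its largest population SD, 2.5, when half score 0 and half score 5. A sample SD of 2.56 can occur in a very small pilot (the maximum is 2.58 with 15 people, 2.67 with 7 or 8) but not as a population value. Using 2.5 changes little: 282 per group, 22% pairwise. A smaller SD changes more. At 51.5 per arm, an assumed common SD of 1.96, 1.5 or 1.2 gives 28%, 43% or 61%.

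**8. More people?** If all 317 were evaluable (79 per arm), pairwise power before clustering is 31% or 67% on the two premises. Assuming 20 per class less 35% (28 × 20 × 0.65/4 = 91 per arm), it is 35% or 73%.

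**The case against.** **The sized contrast is identifiable.** A reader might infer that the plan leaves open which contrast the 80% belongs to. The documents do not support that: the SDs and the difference are labelled oral guidance and video, which fits the 14 v 14 split in phase II. What is missing is a primary contrast in the Statistical analysis section. This stands.

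**The plan never claims 80% for the App.** Also true. The misreading is a risk created by silence, not a statement in the text. The 0.53 is an oral v video difference, so using it for App comparisons is illustrative.

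**The low figures rest on doubtful SDs.** This stands. The 22% depends on a 15-person pilot and an SD that the score could not have in a population. It should not be read as the trial's actual power.

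**The 49% is not a ceiling.** A reader might take it as the most that a pairwise test could have. It holds two-sided at 51.5 per arm with 108 granted. The plan's 216 gives 51%, a one-sided test at 51.5 gives 53%, and larger samples or smaller SDs give more. None of the values shown reaches 80%.

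**The pooled contrast may be close to target.** If 108 is granted, pooled oral v video has 78% before clustering. That is a fair reply on the number of arms. It does not rescue the 80%, because 108 does not follow from the stated inputs and an assumed ICC of 0.02 to 0.10 lowers 78% to 73% to 57%.

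**Collection ended in December 2016.** Retrospective power for the App would add little. That favours confidence intervals as the remedy for those comparisons.

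**Conclusion.** The power statement is wrong as written and should be fixed. By the plan's own inputs, 108 per group gives about 40% two-sided, and 80% needs about 291 (229 one-sided). This needs no assumption beyond the standard formula. The 317 matches neither usual way of allowing for 35% loss. Clustering is left out although classes are randomised.

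Separately, the figure does not extend to the four-arm or pairwise tests. Before clustering, at 51.5 to 54 evaluable per arm and 0.53 points, two-sided pairwise power is about 22% to 23% from the stated SDs, or 49% to 51% if 108 is granted. Pooled oral v video at 103 per side has 39% or 78%, falling to 35% to 26% or 73% to 57% at the assumed ICCs.

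The size of the shortfall depends on the true SD, the ICC and the number evaluable. The documents settle none of these: the SDs are doubtful, no ICC is given, and the number enrolled is not stated apart from the 317. The errors in the calculation, the missing design effect and the lack of cover for the four-arm tests do not depend on them.

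**What to change.** No further enrolment is needed.

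1. State that the calculation refers only to pooled oral guidance v video (14 v 14 classes). Check the pilot SDs against the 0 to 5 range, and correct the 108 and the 317.
2. Withdraw the 80%. Restate the power or detectable difference of that contrast from the checked SDs and the actual number evaluable, with design effect 1 + (m − 1) × ICC, where m is the number evaluable per class, over a stated ICC range.
3. Label the four-arm and pairwise comparisons, including those that bear on the App, as not powered and exploratory. Report effect estimates with cluster-adjusted confidence intervals, so that a null App result is not read as evidence of no effect.

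The cost is revised wording and a little more analysis of data already collected. The stated power will look less favourable.

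### The 80% power is for oral v video at 108 per group, but the four-arm design leaves about 54 per arm for that comparison without the App

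*Combined protocol and SAP*

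**What the plan says.** All references are to the combined protocol and SAP.

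- **Study population and sample size.** The method is a two-group one: "The comparison between two independent groups was used for the sample calculation considering the unequal variances". The inputs are pilot values for oral guidance and video: "the standard deviation of the KS from the 'oral guidance' group was 2.56, while in the 'video' group it was 1.96", and "the difference detected between the groups was 0.53 points in the knowledge score". At 5% significance and 80% power, "a sample value of 108 individuals was found for each group, totaling 216 participants". A 35% loss is then allowed for, giving 317. The App does not enter the calculation. The same section declares four arms at 1:1:1:1, with classes as the randomised unit.
- **Interventions.** In Phase II, 14 classes receive oral guidance and 14 receive video. In Phase III they become four groups of seven, and "for two of them, a smartphone App was developed so that reinforcement messages were sent during a period of 30 days". The questionnaire is described at Phase I and then once more: "Shortly after this period (phase IV), the participants answered the questionnaire again (follow-up test) and were reassessed clinically". The App sends 60 messages over 30 days, in daily pairs: "the first with information in written form and the second in the form of videos, which had an average" length of one minute.
- **Statistical analysis.** KS is compared among the intervention groups by Kruskal-Wallis and Mann-Whitney tests. No comparison pooled over App use, and no factorial model, is named.

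**The concern.** The calculation sizes two groups and the trial has four. Because 216 is the whole evaluable sample, 108 per group can only be the complete oral and video halves. By the one follow-up test that the text describes, those halves have apparently each been split by App use. The comparison that resembles the pilot, guidance without the App, is therefore made on half of each side.

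A reader who takes the stated 80% at face value will believe that the trial had a good chance of detecting a 0.53-point gap between oral guidance and video. If the comparison is made between the two App-free arms, that chance is much lower, and a non-significant result says little about whether the methods differ.

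**Working it through.** **Inputs from the document:** SDs 2.56 and 1.96; difference 0.53; 5% significance (taken as two-sided, since sidedness is not stated); 80% power; 108 per group; 35% loss; 317 enrolled; 28 classes in four groups of seven; about 20 adolescents per classroom session.

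**1. The plan's own figure.** n per group = (SD₁² + SD₂²)(z₀.₉₇₅ + z₀.₈₀)² / δ² = (6.5536 + 3.8416) × (1.960 + 0.842)² / 0.53² = 10.395 × 7.849 / 0.2809 = 290.5, so 291. One-sided it is 229. The printed 108 does not follow from the stated method and inputs. On the printed SDs, power at 108 per group is Φ(0.53/√(10.395/108) − 1.960) = Φ(1.708 − 1.960) = 40%. That is a separate fault, so both starting points are carried below: the plan's premise (80% at 108) and the printed SDs (40% at 108).

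**2. Numbers in the App-free comparison.** Assume that one oral and one video group received the App.
- From the evaluable total: 216/4 = 54 per arm.
- From enrolment: 317/4 ≈ 79, and 79.25 × 0.65 ≈ 52 per arm.
- Upper case, if all 28 classes supplied about 20 pupils: 7 × 20 = 140, and 140 × 0.65 = 91 per arm.

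**3. Power at those numbers.** On the plan's premise, power = Φ(2.802 × √(n/108) − 1.960). On the printed SDs, power = Φ(0.53/√(10.395/n) − 1.960).

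| Evaluable per arm | Plan's premise | Printed SDs |
|---|---|---|
| 108 (as sized) | 80% | 40% |
| 91 | Φ(2.572 − 1.960) = 73% | Φ(1.568 − 1.960) = 35% |
| 54 | Φ(1.981 − 1.960) = 51% | Φ(1.208 − 1.960) = 23% |

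These figures ignore clustering by class, so they are optimistic.

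**4. Pooling over App use.** This gives 108 v 108. Let r be the oral-video gap in App classes as a fraction of the gap without the App. The pooled gap is 0.53 × (1 + r)/2. The documents give no value for r, so the range is illustrative only.

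| r | Pooled gap | Plan's premise | Printed SDs |
|---|---|---|---|
| 1.5 | 0.66 | 94% | 57% |
| 1 | 0.53 | 80% | 40% |
| 0.5 | 0.40 | 56% | 25% |
| 0 | 0.27 | 29% | 13% |

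Pooling keeps the sized difference only at r = 1, when the App leaves the gap unchanged.

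**5. For scale.** Holding 108 evaluable in each of four arms would need 432 evaluable, or 432/0.65 = 665 enrolled.

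**The case against.** The strongest reply is that the App-free comparison survives. In a four-arm trial, oral alone v video alone is an ordinary pairwise comparison with no App on either side, and it is unbiased by the App. That stands. The fault is in the number of participants and the stated power, not in whether the comparison can be made.

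A reader might go further and infer that the App masks the oral v video difference: its 60/2 = 30 videos of about a minute add up to roughly 30 minutes, against 14 for the classroom video, so the gap must shrink. The documents do not support this. On the assumed split, both sides get the same App, so only a change in the gap caused by the App would matter, and nothing in the text shows its size or direction. The App could also widen the gap. The dilution figures in step 4 further depend on a pooled comparison that the analysis section does not name.

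Three more reservations stand:
- That one App group came from each side is inferred, since the text speaks only of two of the four groups.
- Figure 1 is not available here. The Interventions section describes four phases, while the Oral clinical examination section places the second examination in a Phase V at 20 weeks. A further knowledge test shown only in the figure cannot be excluded.
- Recruitment may have exceeded the plan. At 140 per arm, a loss below about 23% (1 − 108/140) would reach 108 per arm.

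**Conclusion.** The concern holds as a mismatch between the stated power and the design. The 108 per group and 80% belong to a two-group comparison. At the planned size, the App-free version of that comparison has about 54 evaluable per arm, with power of about 51% on the plan's own premise or 23% on the printed SDs. With about 91 per arm the figures would be 73% and 35%. This rests on an even split of the App between oral and video classes, a two-sided test, a normal approximation and no clustering.

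It does not follow that the oral v video comparison is lost, or that the App has diluted it. A comparison pooled over App use would have the sized number, but it estimates a different quantity and is not specified. The failure of 108 to follow from its inputs and the absence of any allowance for clustering are separate problems. Correcting either would not bring the two-group sizing into line with the four-arm design.

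**What to change.** 1. **Study population and sample size:** state that the 108 per group and 80% power apply to a comparison of two groups. Give the lower power for pairwise comparisons among the four arms at the planned number per arm.
2. **Interventions:** say explicitly which two of the four groups received the App, and list every time at which KS was taken, consistent with Figure 1.
3. **Statistical analysis:** say whether oral v video means the App-free pairwise comparison or the comparison pooled over App use. If pooled, label it as averaged over App use.
4. **Reporting:** do not present a non-significant result from either comparison as evidence that oral guidance and video are equivalent.

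The cost is wording, and a less favourable stated power. No new data are needed, which matters because the study ran from July to December 2016. A KS test at the end of Phase II, before the App starts, is an option only for a repeat study. It would compare all 14 oral with all 14 video classes, but it would measure immediate knowledge rather than knowledge after 30 days, and it would add an exposure to the five test items. The document does not say when the pilot KS was taken, so such a test cannot be assumed to match the sized comparison.
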